7.4.2.2 Dose Reductions/Escalations

There will be no dose escalations or reductions of nivolumab allowed. Subjects in Arm 1 may be dosed no less than 12 days from the previous dose; subjects in Arm 2 may be dosed no less than 26 days from the previous dose.

Nivolumab infusion can be interrupted and/or the IV infusion rate can be reduced. This information will be retrieved from CRF dosing pages.

The following will be summarized by treatment arm:

- Number of subjects with at least one infusion with the IV rate reduced along with the reason of the rate reduction
- Number of subjects with at least one dose infusion interrupted along with the reason for the interruption and the number of infusions interrupted per subject.

A by-subject listing of study drug administered will be provided. A batch listing number will be also provided.

[REDACTED]

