#### **4.5 Selection and Timing of Dose for Each Subject**

Subjects will be enrolled after receiving up to 12 months (52 weeks) of nivolumab therapy at 240 mg or 3 mg/kg Q2W and after achieving a CR, PR, or SD, confirmed on 2 consecutive tumor assessments.

Subjects in Arm 1 will receive 240 mg of nivolumab intravenously as a 30-minute ( $\pm$  5 minutes) IV infusion on Day 1 of each treatment cycle every 2 weeks, until progression, unacceptable toxicity, withdrawal of consent, or the subject reaches a maximum of 2 years from the first on-study dose, or the study ends, whichever occurs first. In this arm, each 14-day dosing period will constitute a cycle.

Subjects in Arm 2 will receive 480 mg nivolumab as a 30-minute ( $\pm$  5 minutes) IV infusion on Day 1 of each treatment cycle every 4 weeks until progression, unacceptable toxicity, withdrawal of consent, or the subject reaches a maximum of 2 years from the first on-study dose, whichever occurs first. In this arm, each 28-day dosing period will constitute a cycle.

Subjects in Arm 1 may be dosed no less than 12 days from the previous dose; subjects in Arm 2 may be dosed no less than 26 days from the previous dose.

No dose escalations or reductions of nivolumab are allowed. There are no premedications recommended for nivolumab until infusion reactions have been observed in the subject. Subjects should be carefully monitored for infusion reactions during nivolumab administration. If an acute infusion reaction is noted, subjects should be managed according to [Section 4.5.5](#).

Dose delay criteria, criteria to resume treatment, and dose discontinuation criteria can be found in [Section 4.5.1](#), [Section 4.5.2](#), and [Section 4.5.3](#), respectively.

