2.1 Study Design

This is an open-label, randomized phase IIIb/IV dose frequency optimization trial in adult patients with advanced/metastatic (Stage IIIb/IV) NSCLC (non-Sq and Sq). Subjects will have received approximately up to 12 months (52 weeks) of nivolumab therapy at either 3 mg/kg or 240 mg every 2 weeks and achieved a complete response (CR), partial response (PR), or stable disease (SD) as evidenced by 2 consecutive tumor assessments prior to enrollment. At enrollment, subjects will be randomized 1:1 to receive either 240 mg every 2 weeks (Arm 1) or 480 mg every 4 weeks (Arm 2). Randomization will be stratified by histology (Sq vs. Non-Sq) and response criteria to pre-study nivolumab at randomization (CR or PR vs. SD). For subjects receiving nivolumab 240 mg every 2 weeks, each 14-day dosing period will constitute a cycle. For subjects receiving nivolumab 480 mg every 4 weeks, each 28-day dosing period will constitute a cycle.

Subjects will continue treatment until disease progression or unacceptable toxicity for a maximum of 2 years from first randomized dose. The follow-up period begins when the decision to permanently discontinue a subject from study therapy is made (no further treatment or retreatment with nivolumab is anticipated). All subjects who discontinue study drug should comply with protocol specified follow-up procedures as outlined in Section 5 of the Clinical Protocol until death or the conclusion of the study. The only exception to this requirement is when a subject withdraws consent for all study procedures including post-treatment study follow-up or loses the ability to consent freely.

The study design schematic is presented in [Figure 2.1-1](#).

Figure 2.1-1: Study Schema

Each patient’s last study visit will be defined as the last on-treatment or follow-up visit that occurs prior to the date of 3 years after the initiation of randomized therapy. The study will be completed no later than 3 years after the last subject’s first visit.

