7.4.2 Modifications of Study Therapy

7.4.2.1 Dose delays

Treatment may be delayed for up to a maximum of 6 weeks from the previous dose. Dose interruption of nivolumab which results in treatment interruption of >6 weeks will require treatment discontinuation, with the following exceptions: dosing interruptions to allow for prolonged steroid tapers to manage drug-related adverse events; dosing interruptions for non-drug-related reasons if approved by the medical monitor. Prior to re-initiating treatment in a subject with a dosing interruption lasting >6 weeks, the Medical Monitor must be consulted. A dose will be considered as actually delayed if the delay exceeds 2 days (i.e., greater than or equal to 3 days from scheduled dosing date). The length of delay is defined as (duration of previous cycle in days – 14) for Arm 1 and (duration of previous cycle in days – 28) for Arm 2. Dose delays will be divided into following categories: 3 - <8 days, 8 - <15 days, 15 - <28, 28 - <42, >=42 days. Reason for dose delay will be retrieved from the case report form (CRF) dosing pages.

The following parameters will be summarized by treatment arm:

- Number of dose delayed per subject, length of delay and reason for dose delay
- Number of subjects with at least one dose delay along with reason for the dose delay.

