7.6.4 Adverse Events Leading to Dose Delay

AEs leading to dose delay will be summarized for all treated subjects by treatment arm:

- Overall summary of AEs leading to dose delay by worst CTC grade (grade 1, 2, 3, 4, 5, unknown) presented by SOC/PT

The analysis will be conducted using the 30-day safety window and repeated using the 100-day safety window.

By-subject listing of AEs leading to dose delay will be provided.

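### SAP 7.4.2.2 reports infusion interruptions and rate reductions per subject only, although Arm 1 has about twice as many infusions as Arm 2, so a difference in risk per infusion can be partly or wholly hidden

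*SAP*

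**What the plan says.** SAP 2.1 sets the schedules: "For subjects receiving nivolumab 240 mg every 2 weeks, each 14-day dosing period will constitute a cycle" and "For subjects receiving nivolumab 480 mg every 4 weeks, each 28-day dosing period will constitute a cycle". Protocol 4.5 gives both doses over the same infusion time. For Arm 2 it reads "Subjects in Arm 2 will receive 480 mg nivolumab as a 30-minute", and Arm 1 receives 240 mg over the same 30 minutes.

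For infusion modifications, SAP 7.4.2.2 plans two summaries by arm. One is "Number of subjects with at least one infusion with the IV rate reduced along with the reason of the rate reduction". The other covers subjects with an interrupted infusion, with reasons and the number of interruptions per subject. The number of rate-reduced infusions is not summarised, and nothing is divided by infusions given.

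For delays, SAP 7.4.2.1 plans the number of delays per subject and "Number of subjects with at least one dose delay along with reason for the dose delay". SAP 7.6.4 adds "AEs leading to dose delay will be summarized for all treated subjects by treatment arm", by worst grade.

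Related summaries elsewhere are doses received and relative dose intensity (SAP 7.4.1) and exposure-adjusted rates of AE occurrences (SAP 7.6.10). None is a per-infusion rate of interruptions or rate reductions.

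**The concern.** The regimens differ in two ways that bear on infusion tolerability. Arm 1 has about twice as many occasions on which an infusion can be interrupted or slowed. Arm 2 delivers 480 mg instead of 240 mg in 30 minutes, and Protocol 1.1 expects steady-state peaks about 20% higher than with 3 mg/kg every 2 weeks.

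A per-subject proportion depends on both the number of infusions and the risk of each one. Two questions therefore share one figure: how often a patient on the regimen is troubled, and whether a 480 mg infusion is harder to tolerate than a 240 mg infusion. The planned tables answer the first. On the second, equal risk per infusion would look like worse tolerability on Q2W, and a higher risk per infusion on Q4W could look like no difference. Protocol 4.5.5 handles Grade 2 infusion reactions by stopping the infusion and restarting at a reduced rate, so these events record infusion tolerability directly.

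**Working it through.** The plan states no expected figure for these summaries, so there is none to reproduce.

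**Inputs from the documents.** Cycle lengths are 14 and 28 days (SAP 2.1). Infusions per year are 365.25/14 = 26.1 and 365.25/28 = 13.0, a ratio of 2. Dose rates are 240/30 = 8 mg/min and 480/30 = 16 mg/min (Protocol 4.5). SAP 6.2 gives a 5-year treatment maximum and SAP 2.1 gives 2 years. These need reconciling, but the ratio does not depend on them.

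**Assumptions.** The documents give no risk *p* per infusion, so a range is shown. Time on treatment is equal in the two arms.

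**1. Independent infusions.** P(at least one event) = 1 − (1 − *p*)^*k*, with *k* = 26 or 13 at 12 months.

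| *p* in Arm 1 | Arm 1 | Arm 2, same *p* | Arm 2, doubled *p* |
|---|---|---|---|
| 0.5% | 12.2% | 6.3% | 12.2% |
| 1% | 23.0% | 12.2% | 23.1% |
| 2% | 40.9% | 23.1% | 41.2% |
| 5% | 73.6% | 48.7% | 74.6% |

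With 6 months on treatment and *p* = 0.5%, the figures are 6.3%, 3.2% and 6.3%, so the pattern does not need a full year.

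The planned count of interruptions per subject does not separate the two questions either. At 0.5% its mean is 26 × 0.005 = 0.13 versus 13 × 0.005 = 0.065 with equal risk, and 0.13 versus 13 × 0.01 = 0.13 with doubled risk. Per 100 infusions given, the same cases read 0.5 versus 0.5 and 0.5 versus 1.0.

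**2. Clustering within subjects.** Let risk vary between subjects (beta-binomial, mean *p*, intraclass correlation ρ). Then P(at least one) = 1 − ∏ (B + j)/(A + B + j) for j = 0 to *k* − 1, with A = *p*(1/ρ − 1) and B = (1 − *p*)(1/ρ − 1). At *p* = 1% and 12 months:

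| ρ | Arm 1 | Arm 2, same *p* | Arm 2, doubled *p* |
|---|---|---|---|
| 0 | 23.0% | 12.2% | 23.1% |
| 0.05 | 15.4% | 9.7% | 18.4% |
| 0.3 | 6.1% | 4.7% | 9.3% |

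The spurious gap at equal risk narrows, and a doubled risk becomes partly visible: a ratio of 18.4/15.4 = 1.19 at ρ = 0.05 and 9.3/6.1 = 1.52 at ρ = 0.3, against a true ratio of 2.

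**3. Dose delays.** Assume AEs arise at the same rate over calendar time in both arms, with onset uniform within the cycle, exponential duration with mean *m* days, and a delay counted from 3 days past due (SAP 7.4.2.1). The chance that an AE causes a delay is P(T) = (*m*/T)[exp(−3/*m*) − exp(−(T + 3)/*m*)], for T = 14 or 28. Delays per subject are proportional to P(T). Delays per dose due are proportional to T × P(T), so their Arm 2:Arm 1 ratio is 2 divided by P(14)/P(28).

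| *m* (days) | P(14) | P(28) | Per subject, Arm 1:Arm 2 | Per dose due, Arm 2:Arm 1 |
|---|---|---|---|---|
| 7 | 0.28 | 0.16 | 1.76 | 1.14 |
| 10 | 0.40 | 0.25 | 1.60 | 1.25 |
| 14 | 0.51 | 0.35 | 1.46 | 1.37 |
| 21 | 0.63 | 0.48 | 1.32 | 1.51 |

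Neither measure is neutral. Relative dose intensity is neutral for total delay: 28 days of delay over a planned 364 days gives 364/392 = 92.9% in both arms.

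**The case against.** The trial compares regimens. A patient with more interruptions because of more infusions does carry more burden, and a per-subject proportion measures that correctly. This stands: the per-subject tables should stay, and a reader should not infer that they are wrong or that they favour Q4W improperly. They answer one question and leave another open.

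A reader might also infer that a doubled risk at 480 mg would be invisible. Exact cancellation needs a risk ratio of exactly 2 (matching 26/13) and independent infusions. Independence is doubtful here: subjects have already tolerated nivolumab before entry (Protocol 3.3.1), premedication is recommended after Grade 1 or 2 reactions, and Grade 3 or 4 reactions end treatment (Protocol 4.5.5). With clustering, masking is partial. Protocol 1.1 also describes the exposure-response relationship for safety as flat, so the documents give no reason to expect a doubling.

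A third tempting inference is that delays need the same remedy, with delays per dose due as the comparison between arms. The third calculation does not support that: with equal toxicity this measure runs against Arm 2, and at a mean duration of 21 days it is further from neutral (1.51) than the per-subject measure (1.32).

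Finally, a crude interruption rate can be derived from interruptions per subject and doses received. That is true for interruptions. Rate reductions have no summarised event count, so at best the by-subject listing would supply one.

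**Conclusion.** The point holds for infusion interruptions and rate reductions. No visible section plans a per-infusion rate, and the per-subject figures cannot separate infusion frequency from risk per infusion. With independent infusions over 12 months, an equal 0.5% risk reads 12.2% versus 6.3%, and a doubled risk reads 12.2% versus 12.2%. With an intraclass correlation of 0.05 and a 1% risk, the figures are 15.4% versus 9.7% (equal) and 15.4% versus 18.4% (doubled). The size rests on assumed risks and equal time on treatment; the two-fold difference in scheduled infusions comes from the documents.

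For dose delays, the per-subject measure runs about 1.3 to 1.8 times higher in Arm 1 under equal time-driven toxicity, and delays per dose due about 1.1 to 1.5 times higher in Arm 2. Neither should stand alone as the comparison.

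These are descriptive safety and exposure tables, and the PFS analyses are unaffected. The redacted SAP 7.4.3, the Core Safety SAP and the table mock-ups in the Data Presentation Plan could not be seen, so a per-infusion table there cannot be excluded.

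**What to change.** In SAP 7.4.2.2, add by arm the number of infusions interrupted and the number rate-reduced, each per 100 infusions given. Add infusion reactions per 100 infusions given to the select AE tables for hypersensitivity/infusion reactions (a select AE category in Protocol Table 1.4.2-1). Any confidence interval should allow for clustering within subjects, for example through a robust variance or by resampling subjects. Keep the per-subject summaries, with a footnote that dosing occasions differ about two-fold between arms.

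In SAP 7.4.2.1 and 7.6.4, do not make delays per dose due the comparison between arms. At most, show it beside the per-subject figures, footnote that the two measures are distorted in opposite directions, and read both alongside relative dose intensity.

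The cost is SAP wording and a few table columns. SAP 7.4.2.2 already takes interruptions and rate reductions from the CRF dosing pages, and reactions come from the AE data, so no new data collection is needed.

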7.4.4 Subsequent Therapy

Subsequent therapies will be summarized and listed by:

- Frequency of subsequent therapy by type
- By-subject listing of subsequent therapy including all disease-related surgeries and radiotherapies

7.5 Efficacy

7.5.1 Primary Efficacy Analysis

The coprimary objectives will be assessed by PFS rate at 6 months and PFS rate at 12 months. PFS will be summarized by Kaplan-Meier product-limit method for all randomized patients. Median values of PFS, along with two-sided 95% CI using Brookmeyer and Crowley method (a log-log transformed CI for the survivor function $S(t)^{2,3}$, will be calculated for each treatment arm.

The hazard ratios between treatment arms along with the one-sided 95% CI will be produced from a stratified Cox proportional hazard model (by tumour histology [Sq vs. Non-Sq] and response category at randomization [CR or PR vs. SD]).

PFS rates at 6 months and 12 months will be calculated using KM estimates on the PFS curve for each randomized treatment arm. Minimum follow-up must be longer than the time point to generate the rate. The two-sided 95% CIs, adjusted for stratifying factors (by tumor histology (Sq vs. Non-Sq), response criteria (CR or PR vs. SD) using inverse variance weight, for PFS rates at 6 months and 12 months will be calculated for each treatment arm, along with one-sided 95% CI for the difference between the two treatment arms using the Greenwood formula⁴ for variance derivation. Denote $\hat{S}_i(t)$ as an estimate of survival function from Kaplan-Meier estimate and

$\hat{Var}(S_i(t))$ as the variance of estimation for stratum i at time t, respectively, w_i as the weight for

stratum i, defined as
$$\frac{1/\hat{Var}(\hat{S}_i(t))}{\sum_{i=1}^k [1/\hat{Var}(\hat{S}_i(t))]}$$
 where k is the number of strata (k = 4). Then the weighted

survival estimate for PFS rate across all the strata at time t is
$$\sum_{i=1}^k w_i \hat{S}_i(t)$$
 and weighted variance of

estimation is
$$\hat{\sigma}_w^2 = \frac{1}{\sum_{i=1}^k 1/\hat{Var}(\hat{S}_i(t))}$$
. The two-sided 95% CIs for the PFS rates for each treatment

arm will be calculated as
$$\sum_{i=1}^k w_i \hat{S}_i(t) \pm z_{(1-\alpha/2)} \times \hat{\sigma}_w$$
, where $\alpha=0.05$.

The estimated PFS rate difference at time t between two treatment arms is
$$\hat{S}_{E_i}(t) - \hat{S}_{C_i}(t)$$
, where

$\hat{S}_{E_i}(t)$ is the estimated PFS rate for 480 mg every 4 weeks treatment arm (Arm2) for stratum i

and $\hat{S}_{C_i}(t)$ is the estimated PFS rate for 240 mg every 2 weeks treatment arm (Arm 1) for stratum i. The variance for PFS rate difference between two treatment arms at time t for stratum i

is
$$\hat{Var}(\hat{S}_{E_i}(t)) + \hat{Var}(\hat{S}_{C_i}(t))$$
. Denote w_i as the weight for stratum i, defined

as
$$\frac{1/[\hat{Var}(\hat{S}_{E_i}(t)) + \hat{Var}(\hat{S}_{C_i}(t))]}{\sum_{i=1}^k \left\{ 1/[\hat{Var}(\hat{S}_{E_i}(t)) + \hat{Var}(\hat{S}_{C_i}(t))] \right\}}$$
 where k is the number of strata (k = 4). Then the weighted

estimate for PFS rate difference between two treatment arms across all the strata at time t is

$$\sum_{i=1}^k w_i (\hat{S}_{E_i}(t) - \hat{S}_{C_i}(t))$$
 and weighted variance of estimation

is
$$\hat{\sigma}_w^2 = \frac{1}{\sum_{i=1}^k 1/[\hat{Var}(\hat{S}_{E_i}(t)) + \hat{Var}(\hat{S}_{C_i}(t))]}$$
. The one-sided 95% CIs for the difference of PFS rates

between two treatment arms will be calculated as
$$\left(\sum_{i=1}^k w_i (\hat{S}_{E_i}(t) - \hat{S}_{C_i}(t)) - z_\alpha \times \hat{\sigma}_w, 1 \right)$$
, where $\alpha=0.05$.

The source of progression (death vs. progression) will be summarized by treatment arm.

The status of subjects who are censored in the PFS Kaplan-Meier analysis will be tabulated for each treatment group using following categories:

- On-study (on treatment, in follow-up)
- Off-study: (lost to follow-up, withdrew consent, other).
- No baseline tumor assessment and no death
- No on-study tumor assessment and no death

For the 6-month analysis, the 99.3% one-sided adjusted CI around the difference in PFS rates between two treatment arms will be generated using the inverse variance weight method as above where $\alpha=0.007$. If the lower bound of the CI is above -10%, non-inferiority will be claimed.

A 95.2% adjusted CI around the difference in PFS rates at 12 months will be generated using the same approach for 6-month analysis where $\alpha=0.048$. If the lower limit of the CI is above -10%, it is considered that the Arm 2 (Q4W) is non-inferior to Arm 1 (Q2W).

Due to the early stop of enrolment of the study, approximately 350 subjects are expected to be randomized and receive study treatment. With the significant reduction of sample size, there is insufficient power to demonstrate non-inferiority of the two treatment regimens. Hence, the adjustment of alpha between 6 months and 12 months PFS rates will not be conducted. Instead, 95% one-sided confidence interval around the difference of PFS rates will be generated.

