4 ENDPOINTS

4.1 Primary Endpoints

The coprimary endpoints of this trial will be assessed by PFS rate at 6 months after randomization and PFS rate at 1 year after randomization. PFS is defined as the time from the date of randomization to the date of first documented tumor progression determined by the investigator using RECIST 1.1 criteria or death due to any cause, whichever is earlier. Subjects who do not progress or die will be censored on the date of their last evaluable tumor assessment. Clinical deterioration in the absence of unequivocal evidence of progression (per RECIST 1.1) is not considered progression for purposes of determining PFS. Subjects who die without a reported prior progression will be considered to have progressed on the date of their death. Subjects who do not have any on-study tumor assessments and do not die will be censored on the date of randomization. Subjects who receive any subsequent anti-cancer therapy (including on-treatment palliative radio therapy [RT] of non-target bone lesions or central nervous system [CNS] lesions) without a prior reported progression will be censored at the last evaluable tumor assessment prior to or on the date of initiation of the subsequent anti-cancer therapy.

Table 4.1-1: Censoring Scheme for Primary Definition of PFS

Situation	Date of Progression or Censoring	Outcome
No baseline tumor assessments and no death	Randomization	Censored
No on study tumor assessments and no death	Randomization	Censored
New anticancer treatment started without a prior reported progression per RECIST 1.1 or death	Date of last evaluable tumor assessment prior to or on the date of initiation of the subsequent anti-cancer therapy	Censored
Progression per RECIST 1.1 documented at scheduled or unscheduled visit and no new anticancer treatment started before	Date of the first documented tumor progression	Progressed
Subject progression free (per RECIST 1.1) and no new anticancer treatment started	Date of last tumor assessment	Censored
Death without prior progression per RECIST 1.1 and no new anticancer treatment started	Date of death	Progressed

RECIST: Response Evaluation Criteria in Solid Tumors

[figure not shown]
PFS rate at 6 months is the rate from Kaplan-Meier estimate 6 months after randomization; PFS rate at 1 year is the rate from Kaplan-Meier estimate at 1 year after randomization.

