7.1 General Methods

Discrete variables will be summarized with the number and proportion of subjects falling into each category, grouped by treatment arm (with total). Percentages given in these tables will be rounded and therefore, may not always sum to 100%. Continuous variables will be summarized

using the mean, standard deviation (SD), median, minimum and maximum values (summary statistics) by treatment arm (with total). Corresponding by-subject listings will also be created for appropriate populations.

Time to event distribution (i.e. PFS and OS) will be estimated using Kaplan-Meier product-limit techniques. Median survival time along with two-sided 95% confidence interval (CI) will be constructed using Brookmeyer and Crowley method for each treatment arm. Rates at fixed time points (i.e. PFS at 6 months) will be derived from the Kaplan-Meier estimate and corresponding two-sided 95% confidence intervals will be derived for each treatment arm along with one-sided 95% CI for the difference between treatment arms based on Greenwood formula.

The stratified hazard ratio between the 2 treatment arms along with CI will be obtained by fitting a stratified Cox proportional hazard model with the treatment arm variable and stratification factors (tumour histology [Sq. vs. Non-Sq.] and response status at randomization [CR or PR vs. SD]).

Statistical analyses will be carried out using SAS software (SAS Institute, Cary, North Carolina, USA), unless otherwise noted.

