7.5.2 Secondary Efficacy Analyses

PFS rate at 2 years and the corresponding two-sided 95% CI for each treatment arm, along with the one-sided 95% CI for the difference of PFS rate at 2 years between the treatment arms will also be calculated using the same method for PFS rate at 6 months described in the primary efficacy analysis.

OS will be summarized by KM product-limit method for all randomized patients. Median values of OS, along with two-sided 95% CI will be calculated for each treatment arm using the same method as for PFS. The hazard ratios between treatment arms along with the 95% CI will also be produced from a stratified Cox proportional hazard model as for PFS. Survival rates at 6, 12, 18, 24, and 36 months will be estimated for each treatment arm. Minimum follow-up must be longer than time point to generate the rate. The two-sided 95% CIs for OS rates at each time point for each treatment arm, along with the one-sided 95% CI for the difference of OS rates at each time point between two treatment arms will be calculated using the same method for PFS rates. OS rates at each time point and corresponding two-sided 95% CI for each treatment arm, along with the one-sided 95% CI for the difference of OS rates at each time point between the treatment arms will also be calculated adjusting for stratifying factors - tumor histology and response criteria using the inverse variance weight as for PFS rates.

The status of subjects who are censored in the OS Kaplan-Meier analysis will be tabulated for each treatment arm using following categories:

- on-study (on-treatment and not progressed, on-treatment progressed, in follow-up);
- off-study: (lost to follow-up, withdraw consent, etc.).

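### SAP 7.5.1 builds each arm's 95% CI on an inverse-variance average of four strata, not on the Kaplan-Meier rate it reports; the interval under-covers and has no rule for undefined weights

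*SAP*

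**What the plan says.** SAP 4.1 defines the endpoint without stratum weighting: "PFS rate at 6 months is the rate from Kaplan-Meier estimate 6 months after randomization". SAP 7.1 agrees: "Rates at fixed time points (i.e. PFS at 6 months) will be derived from the Kaplan-Meier estimate and corresponding two-sided 95% confidence intervals". SAP 7.5.1 repeats it: "PFS rates at 6 months and 12 months will be calculated using KM estimates on the PFS curve for each randomized treatment arm".

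The same paragraph of 7.5.1 makes the arm's two-sided 95% CI "adjusted for stratifying factors (by tumor histology (Sq vs. Non-Sq), response criteria (CR or PR vs. SD) using inverse variance weight". With S_i the KM estimate in stratum i and Var_i its Greenwood variance, w_i is proportional to 1/Var_i. The centre is the sum of w_i S_i, the variance is 1/sum(1/Var_i), and the number of strata is fixed at four. The text calls this centre a weighted "survival estimate for PFS rate across all the strata at time t is", but does not say that it replaces the KM rate.

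SAP 7.5.2 extends the primary method to "PFS rate at 2 years and the corresponding two-sided 95% CI for each treatment arm", and adds OS rates adjusted for "tumor histology and response criteria using the inverse variance weight as for PFS rates". SAP 7.5.3 lists unadjusted arm CIs for PFS at 6 and 12 months as a sensitivity analysis, but none at 2 years. SAP 7.5.5 applies the primary method to subgroups, including the stratification factors themselves. Protocol 8.4.2 asks for stratum-adjusted CIs per regimen but does not specify the weights.

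**The concern.** Inverse-variance pooling suits several estimates of one common quantity. Here the strata include response to pre-study nivolumab (CR/PR versus SD), whose PFS rates may well differ. Four things follow.

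- **Standard error.** A stratum's Greenwood variance is about S(1-S)/n, so each weight depends on the estimate it multiplies. The variance formula ignores this, so the SE is too small at both milestones even with identical strata.
- **Centre.** Relative to its size, a stratum counts more the further its rate lies from 0.5. If stratum rates differ and are not symmetric about 0.5, the centre moves away from the arm's rate. This matters mainly at 6 months (0.63). At 12 months (0.48) the shift is small unless gaps are wide. At 2 years it is downward if the rate is below 0.5.
- **Undefined weights.** The formula fails when a stratum is empty in an arm or its KM estimate is 1 or 0 at the time point. No rule covers this.
- **Subgroups.** Within a histology or response subgroup there cannot be four strata. Plain KM may be meant, but the SAP does not say so.

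At stake are arm CIs in the primary analysis that look more precise than the data allow and, at 6 months, may sit away from the rate printed beside them.

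**Working it through.** **Inputs from the documents.** About 350 subjects randomized 1:1, so 175 per arm; PFS 0.63 at 6 months and 0.48 at 12 months (SAP 5). Squamous share 20% (Protocol 1), or 135/(135+292) = 32% from the nivolumab arms of the two planning studies (Protocol 1.4.1).

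**Assumed, because the documents give no figures.** CR/PR share 40% (30-60% also run); CR/PR and SD rates chosen so that the arm average equals the plan's rate.

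**Planning figure first.** With margin 0.10, one-sided alpha 0.048, 80% power and 0.48 in both arms: n = (1.665 + 0.842)^2 x 2 x 0.48 x 0.52 / 0.10^2 = 314 per arm, against 310 stated. The planning rates are therefore being read as intended.

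**Shift of the centre, with weights at their true values.** At 40% CR/PR an arm has 70 CR/PR and 105 SD subjects.
- 6 months, 0.80 and 0.517: 70/(0.80 x 0.20) = 437.5 and 105/(0.517 x 0.483) = 420.5. Centre = (437.5 x 0.80 + 420.5 x 0.517)/858.0 = 0.661, against 0.630. The smaller group gets the larger weight.
- 12 months, 0.65 and 0.367: 70/0.2275 = 307.7 and 105/0.2323 = 452.0. Centre = 0.482, against 0.480.

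Estimating the weights adds a little to the shift and understates the SE.

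**Coverage of the arm's true rate, nominal 95%.** Binomial simulation, 200,000 trials per cell, fixed stratum sizes (14/56/21/84 and 22/48/34/71), counting only trials where the formula is defined:

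| Month | CR/PR, SD rates | Coverage | Bias (points) | Mean SE / true SD |
|---|---|---|---|---|
| 6 | identical | 92-93% | +0.5 | 0.93-0.94 |
| 6 | 0.70, 0.583 | 90% | +1.1 | 0.88 |
| 6 | 0.75, 0.55 | 83% | +2.2 | 0.79-0.81 |
| 6 | 0.80, 0.517 | 67-69% | +4.0 to +4.3 | 0.67-0.71 |
| 12 | identical | 93% | -0.1 | 0.94-0.95 |
| 12 | 0.55, 0.433 | 92-93% | 0.0 | 0.91-0.92 |
| 12 | 0.60, 0.40 | 90-91% | +0.1 | 0.85-0.86 |
| 12 | 0.65, 0.367 | 87% | +0.4 | 0.77-0.78 |

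In these cells whole-arm KM with Greenwood variance covers 94-96% and stratum-size weights 94-95%. Over CR/PR shares of 30-60%, the SAP formula at gaps of 0, 11.7, 20 and 28.3 points covers 92-93%, 89-91%, 80-88% and 61-82% at 6 months, and 93-94%, 92-93%, 90-91% and 85-87% at 12 months. Its coverage of its own weighted-average target is 80-93%.

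**Checks with event times.** Exponential times, 10% per year dropout and full KM/Greenwood (4,000 trials per cell) give 0.920-0.924 (identical) and 0.68-0.71 (28 points) at 6 months, and 0.935 and 0.865-0.871 at 12 months; whole-arm KM covers 0.947-0.962. A separate piecewise-exponential run with other stratum mixes and an added 5-point histology gap where responder gaps were assumed gives 91.7-92.4% and 92.1-93.3% with identical strata. At a 15-point responder gap it gives 87.9-89.9% and 91.0-91.4%. Across that run's scenarios, with gaps up to 35 points, whole-arm KM covers 93.9-95.5% and size weights 92.4-94.8%.

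**2-year PFS.** Extending the plan's 6-12-month hazard: 0.48 x (0.48/0.63)^2 = 0.28. Coverage is 91% (bias -0.9 points) with identical strata, 87-88% (-1.5) at 0.35 and 0.233, and 79% (-2.7) at 0.40 and 0.20. Over rates of 0.25-0.35: 90-92%, 85-91% and 73-87%.

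**Undefined weights.** A squamous CR/PR stratum of 14 with rate 0.80 has no event with probability 0.80^14 = 4.4%. Across the PFS cells at 6 and 12 months the arm formula fails in 0-4.4% of trials and the difference in 0-0.2%. At an assumed OS of 0.90, 0.90^14 = 23% and 0.90^21 = 11% for the two smallest strata. The adjusted arm CI then fails in 13-32% of trials and the difference in 1-6%. After collapsing histology within response, failures were 0 of 200,000.

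**Between-arm difference, equal arms.** One-sided error 5.4-5.7% against 5%.

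**The case against.** The strongest reply is that no conclusion rests on these intervals. The coprimary objective compares arms, the planned inference is the one-sided CI for the difference, and that CI has its own weights and is near nominal (about 5.2-5.4% error also at a true difference of -10 points). Unadjusted arm CIs exist at 6 and 12 months, and the adjusted OS CIs are additional to other OS intervals. This all stands, and it limits the severity.

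The text can also be read as reporting the weighted rate with its own CI. On that reading the KM rate would not appear beside an interval that excludes it, which otherwise happens at 6 months in 18-20% of trials at the 28-point gap, 3-4% at 20 points and under 1% at 12 points. The under-coverage remains on either reading.

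The large deficits need assumed gaps of 20 points or more. That is true; the 2-3 point deficit with identical strata does not.

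The 2-year rate could be higher than 0.28. The planning studies' 1- to 2-year falls (19% to 12%, 21% to 16%) give 0.48 x 12/19 = 0.30 and 0.48 x 16/21 = 0.37. At 0.33-0.37 with identical strata coverage is 92-93%, so the deficit shrinks but does not vanish.

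Three points about the remedy also stand: whole-arm KM drops the arm-level adjustment in Protocol 8.4.2; size weights still need a rule for an empty stratum; and at OS 0.90 plain Greenwood on whole-arm KM covers only about 92.5%, against 95.6-95.7% with log-log.

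**Conclusion.** The concern holds: the arm-level CI rule is wrong as written and should be fixed. What rests on no assumption about stratum gaps is coverage of about 92-93% at 6 months and 93% at 12 months instead of 95%, at 175 per arm and the planning rates. How much worse it gets depends on the CR/PR-SD gap, which the documents do not give: modest at about 12 points, serious at 6 months from 20 points upward. Reporting the weighted average instead of the KM rate does not cure it. The missing rule for undefined weights rarely bites for PFS at 6 and 12 months, but would often bite for adjusted arm OS rates if OS is near 0.90. The coprimary between-arm contrast is not undermined.

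**What to change.** - **SAP 7.5.1 (hence 2-year PFS) and the adjusted arm OS rates in 7.5.2.** Centre each arm's two-sided 95% CI on the reported whole-arm KM rate with its Greenwood or log-log variance, as SAP 7.1 already describes. For high OS rates log-log is the better choice. Record the departure from the arm-level adjustment in Protocol 8.4.2.
- **Alternative that keeps that adjustment.** Use w_i = N_i/N (subjects randomized in stratum i, arms pooled) with variance sum(w_i^2 x Var_i), and report that same estimate with its CI.
- **Between-arm difference.** Inverse-variance weights may stay. Add a rule: if a stratum is empty in an arm, or its combined variance is zero or not estimable at the time point, collapse histology within response category in both arms. Apply the empty-stratum part to size weights too, if they are chosen.
- **SAP 7.5.5.** State that subgroup rates and differences use unstratified KM with Greenwood variance.

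Cost: SAP wording and a small program change, with no new data. Whole-arm KM widens the arm CI by about 1% with identical strata, 2-3% at a 12-point gap and 6-10% at 28 points. Size weights widen it by 0-1% up to 12 points and at most about 4% at 28.
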